GSK3326595 in combination with Pembrolizumab will be explored in subjects with NSCLC, mTCC, melanoma, squamous cell carcinoma of the head and neck (HNSCC) and with squamous cell carcinoma of the cervix.

Cervical cancer is the fourth leading cause of cancer related mortality in women worldwide (Torre, 2015), third in US (Siegel, 2020) and HPV is the driver behind 97% of invasive cervical cancer (Walboomers, 1999). Response rates associated with firstline treatment of recurrent/metastatic cervical cancer ranged from 19% to 36% for cisplatin alone or in combination with paclitaxel respectively (Moore, 2004) to approximately 50% for bevacizumab containing regimens (Tewari, 2017). Median OS values ranged from 8.8 to 9.7 months for cisplatin alone or in combination with paclitaxel respectively (Moore, 2004) to 16.8 months for bevacizumab-containing regimens (Tewari, 2017). Responses to second-line treatments for recurrent/metastatic cervical cancer are limited. In June 2018, pembrolizumab received accelerated approval in the US for the treatment of patients with recurrent/metastatic cervical cancers expressing programmed death ligand (PD-L1) post chemotherapy showing ORR of 14.3% in Combined Percentage Score (CPS)≥1% population (KEYTRUDA (pembrolizumab) [package insert]). Whitehouse Station, NJ: Merck & Co; June 2019). In addition, Pembrolizumab approval in microsatellite instability-high (MSI-H) or mismatch repair deficient solid tumors that have progressed following prior treatment and who have no satisfactory alternative treatment options is appropriate for selected cervical cancer patients.

A number of approaches are currently under clinical exploration including a combination of immune oncology agents (Checkmate 358, NCT02488759) or a combination of immunotherapy and chemotherapy (Keynote 826, NCT03635567). Based on preliminary data from HPV positive cohort of study 204653, some tumor shrinkage was seen in cervical cancer patients. A proposed inclusion of cervical cancer patients that have progressed on or after PD-1 or PD-L1 directed therapy or are PD-1/PD-L1 treatment naïve is based on hypothesis that GSK3326595 may augment pembrolizumab activity in this population when compared to pembrolizumab alone. It is anticipated that patients with CPS<1% and CPS≥1% may obtain benefit from treatment, given this novel combination approach and patients will be enrolled irrespective of PD-L1 status.

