4.3.3.6. NSCLC Cohort

The p53 wild-type NSCLC cohort will be used to estimate the clinical activity for GSK3326595 for this population. The analysis will be performed on a minimum of 10 and maximum of 15 evaluable subjects with confirmed p53 wild-type status. The additional 5 subjects are intended to account for any discrepancies between local p53 testing and central, comprehensive testing to ensure a minimum of 10 evaluable p53 wild-type subjects. Only those evaluable subjects whose central test results confirm p53 wild-type status will be included in the analysis. A subject is evaluable for analysis if they have either progressed or died, withdrawn from the study treatment, or are ongoing and have completed at least two post-baseline disease assessments. A Simon's optimal two stage design will be utilized as a framework for the analysis of this cohort, where one interim analysis will be performed after at least the first 10 treated subjects become evaluable. Please refer to Section 11.5 for details of the design and decision rules.

4.4. Part 3: GSK3326595 + Pembrolizumab Combination Study [Active in all regions, except France]

The primary objective of Part 3 is to evaluate the safety and tolerability of GSK3326595 when administered in combination with pembrolizumab in subjects with select solid tumors. As described in Section 4.4.4, three cohorts will be evaluated. All subjects will receive pembrolizumab at the approved dose (200 mg IV every 3 weeks [q3w]), in combination with GSK3326595 dosed orally at 100 mg QD, 200 mg QD, or 300 mg QD.

All available data from Part 3, including safety, tolerability, efficacy, PK, and PD will be used to select a dose of GSK3326595 to be administered with pembrolizumab in future studies. In order to collect PD data, pre- and on-study biopsies will be required for all subjects. Subjects will receive GSK3326595 at the assigned dose as monotherapy for 14 days, at which time the on-study biopsy will be collected. Subjects will then commence therapy with pembrolizumab administered every 3 weeks. Safety will be

assessed continuously. Cohort(s) may be closed to further enrolment based on toxicity emerging at any time on study, as described in Section 4.4.4.

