4.4.1. Type and Number of Subjects (Part 3)

The study population will be adults, with locally advanced or metastatic NSCLC, melanoma, mTCC, or HNSCC that have failed to respond to treatment (e.g., SD, with subsequent documented progression as per iRECIST, or PD as best response) with prior PD-1 or PD-L1 directed therapy. Subjects who initially responded (e.g., iPR or iCR) to these therapies, then subsequently progressed, will **not** be eligible for participation in Part 3. In addition, squamous cell carcinoma of the cervix patients that have progressed on or after PD-1 or PD-L1 directed therapy or are PD-1/PD-L1 treatment naïve will be enrolled in Part 3. For full details of eligibility criteria, please refer to Section 5.1.

Overall, approximately 30 subjects will be enrolled in Part 3. These subjects will be divided evenly between three cohorts, each receiving a different dose of GSK3326595 in combination with a single dose of pembrolizumab. For details of subject enrolment, please refer to Section 4.4.4 and to the SRM.

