5.4. Examination of Covariates, Other Strata and Subgroups

5.4.1. Covariates and Other Strata

There are no formal plans for any stratification. There are no formal plans for investigating any covariates.

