5.4.2. Examination of Subgroups

There are no formal plans for examining subgroups.

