7.2.3. Confirmed Overall Response Rate (iORR) based on iRECIST for Part 3 Cohort

Overall response rate based on iRECIST (iORR) is defined as the percentage of participants with a best overall response (iBOR) of "immune" complete response iCR or immune partial response iPR (Seymour, 2017). "Immune" best overall response (iBOR) will be summarized by dose levels for Part 3. The derivation of iBOR per iRECIST will be as follows:

- Progressive disease is "confirmed (iCPD) in the new lesion category, if the next imaging assessment, done at 4–8 weeks after iUPD, confirms additional PD, i.e., new lesions or a further increase in new lesion size from iUPD (sum of measures increase in new lesion target ≥5 mm, any increase for new lesion non-target)"(Seymour, 2017).
- iSD, iPR, or iCR can still be assigned if one or more instances of iUPD occurred at a previous visit. However, iCR, iPR, and iSD cannot be assigned if iCPD occurred at a previous visit.

• To be assigned a status of iSD, follow-up disease assessment must have met the iSD criteria at least once after the first dose for a minimum of 49 days.

iBOR takes into account the requirement for confirmation of iCR, iPR, and iPD. If iBOR is iUPD and is confirmed consecutively, iBOR will be termed as iCPD. If iBOR is iUPD but not confirmed, there is no subsequent iSD, iPR, or iCR (e.g., NE or lost follow-up), the iBOR will be termed as iUPD. If iBOR is iUPD but not confirmed and the subject died or discontinued treatment or has initiated new anticancer therapy after this PD assessment, the iBOR will be termed as iCPD.

Examples of scenarios of assignments of confirmed/unconfirmed iBOR (assuming the adjacent timepoints are 28 days apart at least) are provided in the following table:

Casea	Time point	Time point	Time point	Time point	Time point	Confirmed	Unconfirmed
0400	Response 1	Response 2	Response 3	Response 4	Response 5	iBoR	iBoR
1	iCR	iCR	iCR,iPR,	iUPD	iCPD	iCR	iCR
			iUPD, or NE				
2	iUPD	iPR, iSD, or	iCR	iCR	iCR, iPR, iSD, iUPD,	iCR	iCR
		NE			iCPD, or NE		
3	iUPD	iPR	iPR, iCR	iPR, iSD,	iPR, iSD, iUPD, NE,	iPR	iCR
				iUPD, NE, or	or iCPD		
				iCPD			
4	iUPD	iSD or NE	iPR	iSD	iSD,iUPD, iCPD, or	iSD	iPR
					NE		
5	iUPD	iSD	iSD, iUPD, or	iSD, iUPD,	iSD, iUPD, iCPD, or	iSD	iSD
			NE	iCPD, or NE	NE		
6	iUPD	iCPD	Any	Any	Any	iCPD	iCPD
7	iUPD	iUPD	iCPD	Any	Any	iCPD	iCPD
		(no iCPD)					
8	iUPD	NE	NE	NE	NE	iUPD	iUPD
9	iUPD⁵					iCPD	iCPD

Table 11Examples of iBOR Assignments

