15.12.5. Efficacy Tables

		IDSL / Example			
No.	Population	Shell	Title	Programming Notes	Deliverable
Tumor	Response		•		
2.1	All Treated	RE1a	Summary of Investigator Assessed Best Response with Confirmation (RECIST 1.1 Criteria)	By dose level for Part 1, by cohort for Part 2 (all but NHL/GBM) 95% CI is based on Clopper-Pearson exact CI	IA, SAC
2.2	All Treated	RE1a	Summary of Investigator Assessed Best Response with Confirmation (RANO Criteria)	Part 2 GBM cohort 95% CI is based on Clopper-Pearson exact CI	SAC
2.3	All Treated	RE1a	Summary of Investigator Assessed Best Response (Lugano Criteria)	Part 2 NHL cohort 95% CI is based on Clopper-Pearson exact Cl	IA, SAC
2.4	All Treated	RE1a	Summary of Investigator Assessed Best Response with Confirmation (iRECIST Criteria)	Part 3 by dose level 95% CI is based on Clopper-Pearson exact CI	SAC
Time-te	o-Event				
2.5	All Treated	TTE6	Summary of Kaplan-Meier Estimates of Progression-Free Survival at 6 Months (RANO Criteria)	GBM cohort	IA, SAC
2.6	All Treated	TTE1	Summary of Progression-Free Survival Based on Investigator Assessments (RECIST 1.1 Criteria)	By cohort for Part 2 (excluding GBM, NHL)	SAC
2.7	All Treated	TTE1	Summary of Progression-Free Survival Based on Investigator Assessments (RANO Criteria)	GBM cohort	SAC
2.8	All Treated	TTE1	Summary of Progression-Free Survival Based on Investigator Assessments (Lugano Criteria)	NHL cohorts	SAC
2.9	All Treated	TTE1a	Summary of Duration of Response Based on Investigator Assessments (RECIST 1.1 Criteria)	Part 2 ACC TN cohort	SAC

204653

		IDSL / Example			
No.	Population	Shell	Title	Programming Notes	Deliverable
2.10	All Treated	TTE1	Summary of Overall Survival	Part 2 ACC TN cohort and all ACC subjects across parts 1/2	SAC

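### Part 3 response is summarised by dose level only, pooling PD-(L)1-naive with PD-(L)1-pretreated subjects, so the rate is hard to interpret and can distort the informal dose comparison if the naive share differs by dose

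*SAP*

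**What the plan says.** **Who enters.** Protocol Sections 4.4.1 and 5.1 require subjects with NSCLC, mTCC, melanoma or HNSCC to have had SD (followed by progression) or PD as best response to prior PD-(L)1 therapy, and Section 4.4.1 bars those who had responded. Cervical squamous cell carcinoma is treated differently: Section 4.4.1 states that patients who have "progressed on or after PD-1 or PD-L1 directed therapy or are PD-1/PD-L1 treatment naïve will be enrolled in Part 3". The bar on prior responders is not repeated for them.

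**What is known about pembrolizumab alone.** Protocol Section 2.1 cites its accelerated approval in cervical cancer, "post chemotherapy showing ORR of 14.3% in Combined Percentage Score" ≥1% disease. The same section says Part 3 cervical patients are enrolled whatever their PD-L1 status, and gives the hypothesis that GSK3326595 may add to what pembrolizumab does by itself.

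**How response is reported.** SAP Section 7.2.3 says that immune "best overall response (iBOR) will be summarized by dose levels for Part 3". The programming note for Table 2.4 reads "Part 3 by dose level 95% CI is based on Clopper-Pearson exact CI". SAP Section 5.4.1 adds "There are no formal plans for any stratification" and Section 5.4.2 "There are no formal plans for examining subgroups". The Part 3 waterfall and spider plots (Figures 2.14 and 2.18) carry no split by indication or prior therapy, although the corresponding Part 1 plots are coloured by dose and indication. SAP Section 2.3.3, which describes the Part 3 population, leaves out the cervical subjects.

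**What the response data are for.** Protocol Section 4.4 says: "All available data from Part 3, including safety, tolerability, efficacy, PK, and PD will be used to select a dose of GSK3326595" for later studies with pembrolizumab. Clinical response is also a listed endpoint for the combination RP2D.

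**The concern.** A confirmed response in someone whose tumour never responded to earlier PD-(L)1 therapy is more informative about GSK3326595 than one in a PD-(L)1-naive cervical subject, where pembrolizumab alone has documented activity. Pretreated cervical subjects are a third case, because they may include former PD-(L)1 responders. One rate per dose level blends all three.

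Two things follow. First, the rate describes activity in no identifiable population. It answers neither whether GSK3326595 adds to pembrolizumab in cervical cancer nor whether the combination works after PD-(L)1 failure. This holds whenever naive subjects are present, even if their share is the same at every dose. Second, if the share differs between doses, the observed ordering of doses can reflect case mix. Nothing in the plan prevents that: dose levels open one after another from 100 mg, there is no cap or stratification, and cervical subjects were added in Amendment 6, after Part 3 itself arrived in Amendment 4.

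At stake are the description of combination activity, which is a secondary objective, and the efficacy input to the choice of dose.

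**Working it through.** **Plan's own figures.** No sample size, power or error rate is stated for Part 3 response. The only Part 3 operating characteristics are for the safety rule, and they reproduce. For 5+5 subjects at toxicity 0.2, the chance of completing a dose is the sum over x = 0 to 2 of P(X=x), X~Bin(5, 0.2), times P(Y ≤ 3−x), Y~Bin(5, 0.2):

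0.3277×0.9933 + 0.4096×0.9421 + 0.2048×0.7373 = 0.862, against 86.2% in Table 22.

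This confirms the safety design but says nothing about response.

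**Inputs for the illustration.**
- n = 10 per dose level (Protocol Section 4.4.4).
- Naive response rate p: 14.3% (Protocol Section 2.1; CPS≥1%, after chemotherapy). Enrolment ignores PD-L1, so this may be too high; lower values are assumed as a range.
- Refractory response rate r: assumed, 0% or 5%.
- Number of naive subjects k at a dose: not in the documents; k = 5 is assumed, against k = 0.
- GSK3326595 has no effect.

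**Chance of at least one response at a dose:** 1 − (1−p)^k × (1−r)^(10−k).

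- p = 14.3%, r = 0%, k = 5: 1 − 0.857^5 = 0.538. With k = 0 it is 0.
- p = 14.3%, r = 5%, k = 5: 1 − 0.857^5 × 0.95^5 = 1 − 0.4623×0.7738 = 0.642. With k = 0 it is 1 − 0.95^10 = 0.401.
- p = 7%, r = 0%, k = 5: 1 − 0.93^5 = 0.304.

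| Naive rate p | Refractory rate r | 5 naive of 10 | 0 naive of 10 |
|---|---|---|---|
| 14.3% | 0% | 54% | 0% |
| 14.3% | 5% | 64% | 40% |
| 10% | 0% | 41% | 0% |
| 10% | 5% | 54% | 40% |
| 7% | 0% | 30% | 0% |
| 5% | 5% | 40% | 40% |

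The last row is the limiting case: if naive and refractory subjects respond at the same rate, the mix does no harm.

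**Expected pooled iORR:** [k×p + (10−k)×r]/10.
- p = 14.3%, r = 0%: 5×14.3/10 = 7.2% with five naive subjects, 0% with none.
- p = 14.3%, r = 5%: (5×14.3 + 5×5)/10 = 9.7% with five naive subjects, 5.0% with none.
- If k is the same at every dose, the shift between doses is zero and only the level rises.

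**Ordering of two doses, five naive against none (p = 14.3%).** By exact convolution, the dose with naive subjects shows more responses with probability 54% at r = 0%. At r = 5% the probability is 47%, against 18% for the reverse order.

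**Scale of chance variation.** Exact 95% intervals at n = 10 are 0 to 30.8% for 0/10 and 0.3 to 44.5% for 1/10. The shift from case mix lies well inside these.

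**The case against.** The strongest reply is that nothing formal depends on this table. Part 3's primary objective is safety, no hypothesis is tested, and cohorts open on toxicity criteria. Response is one of five informal inputs to a dose for future studies. Recruitment was stopped under Amendment 8 before the first SAP version, so a split changes reporting only. All of this stands, and it limits the weight of the point. It does not remove it: without a test, the displayed rates are what a decision-maker sees.

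A reader might infer that pooling does confound the dose comparison. The documents do not support that. It needs an unequal naive share, and the number of naive subjects is not stated; it could be zero or balanced.

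A reader might also take an all-refractory dose to show no responses. That holds only at a refractory rate of exactly 0%; at 5%, ten such subjects show at least one response 40% of the time.

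It is likewise tempting to rest every statement on activity, and the dose choice, on the refractory subjects alone. That conflicts with Protocol Section 2.1, which states a hypothesis for pretreated or naive cervical patients. Nor would a split isolate the contribution of GSK3326595 in naive subjects, because Part 3 has no pembrolizumab-alone arm.

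Finally, the information is not lost. Tables 1.12, 1.13, 1.23 and 1.24 describe disease and prior therapy by dose, and Listings 26, 28 and 46 give subject-level disease, prior therapy and response. With about 30 subjects the split can be rebuilt by hand. That is a partial answer, since the planned summary table and plots would still show only the blend.

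**Conclusion.** The point holds in a conditional form. The planned Part 3 response summaries pool PD-(L)1-naive cervical, pretreated cervical and PD-(L)1-refractory non-cervical subjects, and none separates them. If naive subjects were enrolled, the pooled iORR mixes populations in which a response means different things. If their share also differs by dose, it can distort the informal dose comparison. Whether either happened cannot be told from the documents.

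The size is modest and depends on assumptions. With no GSK3326595 effect, five naive subjects of ten and a 14.3% naive rate, the expected iORR at a dose rises by 7.2 points (refractory rate 0%) or 4.7 points (9.65 − 5.0, refractory rate 5%). The chance of at least one response is 54% against 0%, or 64% against 40%. At a 7% naive rate and 0% refractory rate it is 30%. These shifts are small beside the exact intervals at n = 10, but they can still change the observed ordering of doses. The change is worth making as a reporting improvement; it does not invalidate Part 3.

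**What to change.** - Keep the by-dose summary in SAP Section 7.2.3 and Table 2.4. Add iORR as n/N with exact confidence interval, by dose, within (a) PD-(L)1-naive cervical, (b) PD-(L)1-pretreated cervical and (c) PD-(L)1-refractory non-cervical subjects.
- Mark this status on Figures 2.14 and 2.18 and in Listing 46.
- Add the cervical population to SAP Section 2.3.3.
- State that the strata are descriptive. If 14.3% is shown as context, say that it applies to CPS≥1% disease after chemotherapy while Part 3 enrolled regardless of PD-L1.

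No new data are needed: prior therapy and best response to it are collected at screening (Protocol Section 8.2). The cost is a grouping variable, some SAP wording, and small strata with wide intervals, some of which may be empty.

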7.2.7. Overall Survival (OS)

Overall survival (OS) is defined as the interval of time (in months) between the start date of treatment and the date of death due to any cause. This will be summarized for the Part 2 ACC TN cohort and all ACC subjects across Part 1 and Part 2.

For subjects who are alive, time of death will be censored at the date of last contact. The date of death should be taken from the *Record of Death* eCRF page. Death on study due to any cause will be included. Survival will be summarized using the Kaplan-Meier method. Estimates of 1st quartile survival, median survival, and 3rd quartile survival will be presented with 95% confidence intervals based on the Brookmeyer-Crowley method (Brookmeyer, 1982).

8. SAFETY ANALYSES

Safety analyses will be based on the All Treated Population, unless otherwise specified. Details of data displays are presented in Appendix 12: List of Data Displays.

8.1. Primary Safety Analyses

8.1.1. Safety Analyses – Part 1 and Part 3

8.1.1.1. Extent of Exposure

Extent of exposure to GSK3326595 and pembrolizumab (applies to Part 3 subjects only) will be summarized separately.

The duration of exposure to study treatment in month (from first day to last day of treatment) will be summarized. Descriptive statistics including mean, median, standard deviation, minimum, and maximum will be calculated for time on study treatment.

The subject's average daily dose, defined as the cumulative dose divided by the duration of exposure for each subject, will be summarized. Subject's average daily dose will only be calculated for GSK3326595. Number of infusions will be provided for pembrolizumab.

Dose reductions will be summarized by number of reductions and reasons for reductions, for GSK3326595 and/or pembrolizumab, where applicable. If there are no reductions, a summary will not be provided. Dose interruptions of GSK3326595 will be summarized by number of interruptions, reasons for the interruptions, and interruption duration (days). The mean, standard deviation, median, minimum value, and maximum value will be computed for the duration of interruptions as well as the number and percentage of the interruptions 1-5, 6-7, >7 days.

Dose delays of pembrolizumab will be summarized by number of delays, reasons for delay and duration of delay (days). The mean, standard deviation, median, minimum value, and maximum value will be computed for the duration of delay as well as the number and percentage of the delays 1-5, 6-7, >7 days.

Dose reductions and interruptions of GSK3326595will be listed separately.

8.1.1.2. Adverse Events

An overview summary of AEs, including counts and percentages of subjects with any AE, AEs related to study treatment, AEs leading to permanent discontinuation of study treatment, AEs leading to dose reductions, AEs leading to dose delays/interruptions, SAEs, SAEs related to study treatment, fatal SAEs, and fatal SAEs related to study treatment will be produced.

The relationship between MedDRA system organ class (SOC), preferred term (PT), and verbatim text will be listed.

Adverse events (AEs) will be graded according to the CTCAE, Version 4.03, [Basch, 2014]. Adverse events will be coded to the preferred term (PT) level using the Medical Dictionary for Regulatory Affairs (MedDRA dictionary).

A summary of number and percentage of subjects with any adverse events by maximum grade will be produced. AEs will be sorted by preferred term in descending order of total incidence. The summary will use the following algorithms for counting the subject:

- **Preferred term row**: Subjects experiencing the same AE preferred term several times with different grades will only be counted once with the maximum grade.
- Any event row: Each subject with at least one adverse event will be counted only once at the maximum grade no matter how many events they have.

In addition, the frequency and percentage of AEs (all grades) will be summarized and displayed in two ways: 1) in descending order of total incidence by PT only and 2) in descending order of total incidence by SOC and PT. In the SOC row, the number of subjects with multiple events under the same system organ class will be counted once.

A separate summary will be provided for study treatment-related AEs. A study treatmentrelated AE is defined as an AE for which the investigator classifies the relationship to study treatment as "Yes". A worst-case scenario approach will be taken to handle missing relatedness data, i.e., the summary table will include events with the relationship to study treatment as 'Yes' or missing. The summary table will be displayed in descending order of total incidence by PT and by maximum grade sorted by PT in descending order of total incidence.

For Part 3 treatment-related AE, the below 3 sets of tables will be generated by system organ class, preferred term, and maximum grade:

- AEs related to GSK3326595
- AEs related or pembrolizumab
- AEs related to GSK3326595 and pembrolizumab

All COVID-19 assessments and symptom assessments for subjects with COVID-19 adverse events will be summarized based on all recorded AEs. There will be no separate definition of "treatment-emergent" AEs.

All AEs will be listed. A listing of subject numbers for individual adverse events will be provided.

A listing of adverse events recorded as dose-limiting toxicities for Part 1 subjects will be provided. Additionally, a summary of the number of patients experiencing DLTs for Part 1 subjects will be provided.

